5.2.3 Additional Endpoints

CCI

6.0 STUDY DESIGN AND DESCRIPTION

This study consists of 2 parts.

Part 1 is an open label initial substudy to explore PK profile of TAK-071 in the presence of light meal and coadministration of scopolamine to determine TAK-071 dose for Part 2, the main study.

Part 2 is the main the study to assess the effects of TAK-071 on scopolamine-induced cognitive impairment.

6.1 Study Design – Part 1

This is a nonrandomized, open-label, 1-treatment, 1-period, 1-sequence phase 1 study to characterize the plasma PK of TAK-071 when administered under the same conditions as in Part 2, the main study, this is in conjunction with scopolamine, and together with a low-calorie, low-fat breakfast in healthy adult male subjects. Approximately 6 healthy subjects will be enrolled in this substudy with a minimum of 4 completers.

A schematic of Part 1, the substudy, design is provided in [Figure 6.a](#).

Figure 6.a Schematic of Study Design – Part 1

Pretreatment Period		Treatment Period		Final Visit	PK Follow-Up	Follow-up
Screening	Check-in	Single Dose/PK	PK	Check-out/PK	PK	Follow-up Telephone Call
Days -28 to -2	Day -1	Day 1	Days 2-4	Day 5	Day 8	Day 12 (±2)
		←—Confinement—→				

Subjects will check-in at the study site on Day -1 and will be confined until the completion of assessments on Day 4. A follow-up PK assessment will be performed on Day 8 and a final follow-up will occur of Day 12 (±2).

Scopolamine will be administered as a single 0.5 mg SC injection.

[figure not shown]
TAK-071 will be administered as a single PO dose (as drug-in-capsule [DIC]) 24 hours before scopolamine administration.

Blood samples for the analysis of TAK-071 plasma concentrations will be obtained at specified time-points up to 168 hours after TAK-071 dosing (144 hours after scopolamine dosing).

Safety and tolerability of TAK-071 in combination with scopolamine will be assessed from physical examination, AEs, clinical laboratory tests, ECGs, etc.

The planned timing of assessments and meals relative to scopolamine dosing in Part 1 is shown in [Figure 6.b](#).

Figure 6.b TAK-071 PK Assessments and Meal Timing Relative to Scopolamine Administration – Part 1 (Days 1 and 2)

6.2 Study Design – Part 2

This is a randomized, double-blind, sponsor unblinded, placebo-controlled, 5-treatment, 5-period, 10-sequence crossover phase 1b proof of mechanism study to evaluate the effects of a single PO administration of TAK-071, a novel M₁R PAM, on scopolamine-induced deficits in cognitive function in healthy adult male subjects.

Approximately 40 subjects are expected to be randomized in this study, with the total of 4 subjects per sequence and with a minimum of 3 completers. A schematic of the study design is provided in [Figure 6.c](#).

Figure 6.c Schematic of Study Design – Part 2

Screening Period	Treatment Periods 1 to 5				Wash-Out Periods 1 to 4	Follow-Up
Screening and Pre-Enrollment Enrichment	Check-in	Baseline PD	Single Dose PK/PD	PK/PD		Follow-up Telephone Call/Visit
Days -56 to -2	Day -1	Day 1	Day 2	Day 3	Days 4 to 20	Day 9 (±2) Period 5
	←—Confinement—→					

6.2.1 Pre-Enrollment Enrichment Screening – Part 2

To ensure that enrolled subjects will show cognitive impairment in the presence of scopolamine but with minimal sedation and/or fatigue, all subjects who meet Screening inclusion/exclusion criteria will be administered an SC dose of scopolamine 0.5 mg.

Pre-enrollment enrichment procedures will be conducted as part of the Screening assessments between 56 and 2 days before Day 1, and the results will be used to accept/reject the subject for enrollment to Part 2, the main study.

Subjects will remain under observation post-scopolamine administration per principal investigator's discretion to ensure that scopolamine-induced effects have worn off and it is safe for the subjects to leave the study center.

Any subject unable to perform the CogState battery after training will be excluded from entering Part 2, the main study.

6.2.2 Treatment Sequences – Part 2

In each period, subjects will check-in at the study site on Day -1 and will be confined until Day 3 (approximately 24 hours postdose of scopolamine or matching placebo).

Subjects will be randomly assigned to 1 of 10 possible treatment sequences (described in [Section 8.1.3](#)) before the first dose of study drug, each consisting of 5 treatment periods ([Table 6.a](#)).

Table 6.a Summary of Treatment Sequences in Study - Part 2

Sequence	Period 1		Period 2		Period 3		Period 4		Period 5
1	A	Minimum 3-week washout	B	Minimum 3-week washout	D	Minimum 3-week washout	E	Minimum 3-week washout	C
2	B		C		E		A		D
3	C		D		A		B		E
4	D		E		B		C		A
5	E		A		C		D		B
6	A		C		B		E		D
7	B		D		C		A		E
8	C		E		D		B		A
9	D		A		E		C		B
10	E		B		A		D		C

A=scopolamine matching placebo SC + TAK-071 matching placebo PO + donepezil matching placebo PO.

B=scopolamine 0.5 mg SC + TAK-071 matching placebo PO + donepezil matching placebo PO.

C=scopolamine 0.5 mg SC + TAK-071 PO + donepezil matching placebo PO.

[figure not shown]
D=scopolamine 0.5 mg SC + TAK-071 PO + donepezil 10 mg PO.

E=scopolamine 0.5 mg SC + TAK-071 matching placebo PO + donepezil 10 mg PO.

A 3-week (21-day) washout between treatment periods is required because of the long $t_{1/2z}$ of donepezil to minimize the potential for carryover effects.

The planned timing of assessments and meals relative to scopolamine dosing is shown in [Figure 6.d](#).

Figure 6.d PK/PD Assessments and Meal Timing Relative to Scopolamine Administration – Part 2

Note: Solid gray PK/PD symbols indicate predose assessments. Numbers inside symbols indicate scheduled times relative to the respective study drug dosing for the PK analyte. Shaded meal symbols indicate low-calorie, low-fat meals; all other meals are standard.

Scopolamine (0.5 mg) or matching placebo will be administered as a single SC injection.

TAK-071 or matching placebo will be administered as a single PO dose (as DIC) 24 hours before scopolamine administration.

The dose of TAK-071 for Part 2 will be selected depending on the results from Part 1 (initial substudy) and the FIH Study TAK-071-1001; however, under no circumstances will the selected TAK-071 dose exceed the maximum tolerated dose (MTD), or if the MTD is not attained, the highest dose tested in the SRD part of the FIH study.

The precise dosing time of TAK-071 relative to scopolamine will be selected to ensure that both drugs reach their anticipated peak effects at approximately the same time to maximize the potential to observe TAK-071 procognitive effects.

Donepezil (10 mg) tablet (overencapsulated) or matching placebo will be administered as a single capsule PO 3 hours before injecting scopolamine to maximize the chances of observing a reversal of the scopolamine-induced cognitive impairment.

Blood samples for the analysis of TAK-071, scopolamine, and donepezil plasma concentrations will be obtained at specified time-points up to 10 hours after scopolamine dosing.

CCI

Information on the safety and tolerability of TAK-071 in combination with scopolamine and/or donepezil will be obtained from treatment periods in which active TAK-071 is administered (Treatments C and D). Safety and tolerability will be obtained during Treatment A for placebo, Treatment B for scopolamine alone, and during Treatment E for donepezil in combination with scopolamine.

6.3 Justification for Study Design, Dose, and Endpoints

6.3.1 Justification for Design for Part 1

An initial substudy (Part 1) has been included since to date TAK-071 has only been administered as a single agent under fasted conditions in Study TAK-071-1001. In the present study, TAK-071 administration will occur 24 hours prior to scopolamine and together with a low-calorie, low-fat breakfast.

Scopolamine has the potential of PK drug-drug interaction as antimuscarinics can inhibit gastrointestinal motility, delay gastric emptying, and prolong gastrointestinal transit time [27,28].

CCI

CCI

6.3.2 Justification for Design for Part 2

This is a randomized, double-blind, sponsor-unblinded, placebo-controlled, 5-treatment, 5-period, 10-sequence crossover phase 1b proof of mechanism study to evaluate the effects of single PO administration of TAK-071, a novel M₁ PAM, on scopolamine-induced deficits in cognitive function in healthy adult male subjects.

The study is being conducted as double-blind and placebo-controlled to avoid subjective bias in the assessment of response. The crossover design was selected to reduce the sample size needed and to minimize intersubject variability.

Scopolamine was selected because it has long been used for the induction of deficits in psychomotor and cognitive function, and the impairments resemble those seen in Alzheimer disease. It is therefore expected that in this study, scopolamine will induce the desired cognitive impairment for the cognitive assessments within a short time with minimal sedation and/or fatigue. To ensure this, pre-enrollment enrichment Screening will be performed for all study subjects who meet Screening inclusion/exclusion criteria after administration of scopolamine 0.5 mg SC. Only subjects who display an acceptable decline in cognitive function with minimal sedation will be allowed to enter the main study.

Donepezil has been selected as the positive control for this study because it is the most frequently used medication for the symptomatic treatment of mild to moderately severe Alzheimer disease at the therapeutic dose of 10 mg once daily (QD).

Combination of donepezil and TAK-071 will provide information about PD effect of an acetylcholinesterase inhibitor in combination with M1PAM measured by amelioration of scopolamine induced cognitive and EEG effects.

CCI

The SC administration of scopolamine has a $t_{1/2z}$ of 3 to 4 hours and reaches C_{max} within 10 to 30 minutes. The cognitive impairment induced by SC administration of scopolamine appears to be maximal approximately 1 to 2 hours after administration and disappears after 6 to 8 hours postinjection, allowing for a minimal but sufficient period of subject supervision before subjects are discharged safely on Day 3. The minimum 21-day washout between the last dose in a period and the first dose in the subsequent period will be sufficient to ensure no drug carryover effect.

TAK-071 and donepezil will be administered 24 and 3 hours, respectively, prior to administration of scopolamine so that the t_{max} of TAK-071 (26 hours in plasma after an 80 mg dose) and donepezil (approximately 3 to 4 hours in plasma) occur at approximately the same time as the maximal scopolamine-induced cognitive impairment effects (approximately 1 to 2 hours after SC administration). The time of administration of TAK-071 relative to scopolamine may be adjusted upon review of emerging PK data from the FIH study.

6.3.3 Justification for Dose

6.3.3.1 *TAK-071*

A high TAK-071 dose will be used in this study to maximize the potential for observing a significant reversal of scopolamine-induced cognitive impairment. The dose of TAK-071 will be selected depending on the results from the FIH Study TAK-071-1001; however, under no circumstances will the selected TAK-071 dose exceed the MTD, or if the MTD is not attained, the highest dose tested in the SRD part of the FIH study. At present, it is planned that the dose for the initial substudy (Part 1) and main study (Part 2) will be 80 mg, this the highest dose tested in an SRD setting to date.

If following a review of the preliminary PK results of Part 1 (initial substudy) reveals that there is an effect of scopolamine and/or food on the plasma exposure of TAK-071 (increase or decrease), the selected TAK-071 dose for Part 2 may be adjusted to ensure that exposures remain on target; and below the lowest no-observed-adverse-effect level (NOAEL) plasma exposure achieved in 4-week GLP animal toxicology studies.

The dosing time of TAK-071 relative to scopolamine will be selected to ensure that both drugs attain their anticipated peak effects at approximately the same time to maximize the potential to observe TAK-071 procognitive effects. Based on preliminary TAK-071 plasma concentration data following a dose of 80 mg indicating that peak concentrations occur at median time of 26 hours postdose, it is planned that dosing of TAK-071 should occur 24 hours prior to scopolamine administration. The precise timing of TAK-071 dosing may be adjusted if warranted based on emerging data.

6.3.3.2 *Donepezil*

Donepezil is the most frequently used medication for the symptomatic treatment of mild to moderately severe Alzheimer disease. Donepezil, administered at the therapeutic dose of 10 mg QD, will serve as a positive control in this study. Donepezil has been previously administered to healthy subjects in the context of multiple phase 1 clinical trials, indicating that single doses of 10 mg are safe and well tolerated in this population [19-22]. In particular, donepezil doses of both 5 and 10 mg have been employed in published [21,22] and unpublished (Study ROF-ALZ_102) scopolamine challenge studies. The higher 10 mg dose is therefore expected to maximize the chances of a successful positive control in the present study.

6.3.3.3 *Scopolamine*

The SC dose of 0.5 mg is a safe and efficacious dose for the purpose of this study's endpoints. This dose has been previously found to result in maximal cognitive impairment with minimal associated sedation and/or fatigue [29]. SC administration will provide the advantage of better reproducibility, or lower variability, in the dynamic changes in the cognitive impairment profile over time. This is important to ensure that most subjects will attain maximal cognitive impairment at approximately the same time (approximately 2 hours postdose).

6.3.4 **Justification for Endpoints**

The CogState GMLT will serve as the primary outcome measure in this study. From a psychometric perspective, the GMLT can be repeated often in an experimental setting and with little or no practice effect. From a construct validity aspect, the GMLT measures a variety of cognitive functions (immediate and short-term memory for visuospatial information), and it is sensitive to the detection of subclinical perseverative errors and slowed information-processing speed.

6.4 **Premature Termination or Suspension of Study or Study Site**

6.4.1 **Criteria for Premature Termination or Suspension of the Study**

The study will be completed as planned unless one or more of the following criteria are satisfied that require temporary suspension or early termination of the study.

- Study discontinuation due to non-safety reasons such as:
 - A finding (eg, PK, PD, efficacy, biologic targets, etc) from another nonclinical or clinical trial using the trial treatment(s) that results in the trial being stopped for a non-safety related reason.
 - Data from comparator(s), drug(s) of the same class, or methodology(ies) used in this trial become available and results in the trial(s) being stopped for a non-safety related reason.
 - The study is stopped due to non-scientific and non-safety reasons, such as slow enrollment.
- Study discontinuation due to safety reasons:
 - Early trial termination due to unanticipated safety concerns arising from clinical or nonclinical trials with the trial treatment(s), comparator(s), drug(s) of the same class or methodology(ies) used in this trial.
 - New information or other evaluation regarding the safety or efficacy of the study drug that indicates a change in the known risk/benefit profile for the product, such that the risk is no longer acceptable for subjects participating in the study.

6.4.2 **Criteria for Premature Termination or Suspension of Study Sites**

A study site may be terminated prematurely or suspended if the site (including the investigator) is found in significant violation of Good Clinical Practice (GCP), protocol, or contractual agreement,

is unable to ensure adequate performance of the study, or as otherwise permitted by the contractual agreement.

6.4.3 Procedures for Premature Termination or Suspension of the Study or the Participation of Study Site(s)

In the event that the sponsor, an institutional review board (IRB), or a regulatory authority elects to terminate or suspend the study or the participation of a study site, a study-specific procedure for early termination or suspension will be provided by the sponsor; the procedure will be followed by applicable study sites during the course of termination or study suspension.

7.0 SELECTION AND DISCONTINUATION/WITHDRAWAL OF SUBJECTS

All entry criteria, including test results, need to be confirmed prior to randomization.

7.1 Inclusion Criteria

1. In the opinion of the investigator, the subject is capable of understanding and complying with protocol requirements.
2. The subject or, when applicable, the subject's legally acceptable representative signs and dates a written, informed consent form and any required privacy authorization prior to the initiation of any study procedures including requesting that a subject fast for any laboratory evaluations.
3. The subject is male and aged 18 to 55 years, inclusive, at the time of informed consent and first study drug dose.
4. The subject weighs at least 50 kg and has a body mass index (BMI) from 18.0 to 30.0 kg/m², inclusive at Screening.
5. A male subject who is nonsterilized* and sexually active with a female partner of childbearing potential* agrees to use barrier method of contraception (eg, condom with or without spermicide)* from signing of informed consent throughout the duration of the study and for 70 days after the last dose of study drug.

* Definitions and highly effective methods of contraception are defined in Section 9.1.9 and reporting responsibilities are defined in Section 9.1.10.

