9.1.9 Contraception and Pregnancy Avoidance Procedure

9.1.9.1 Male Subjects and Their Female Partners

From signing of informed consent, throughout the duration of the study, and for 70 days after the last dose of study drug, nonsterilized** male subjects who are sexually active with a female partner of childbearing potential *must use barrier contraception (eg, condom with or without spermicidal cream or jelly). In addition, they must be advised not to donate sperm during this period. Females of childbearing potential who are partners of male subjects are also advised to use additional contraception as shown in the list containing highly effective/effective contraception below.

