9.1.9.2 Definitions and Procedures for Contraception and Pregnancy Avoidance

The following definitions apply for contraception and pregnancy avoidance procedures.

* A woman is considered a woman of childbearing potential, ie, fertile, following menarche and until becoming post-menopausal unless permanently sterile. Permanent sterilization methods include hysterectomy, and bilateral oophorectomy. A postmenopausal state is defined as no menses for 12 months without an alternative medical cause.

** Sterilized males should be at least 1 year post-bilateral vasectomy and have confirmed that they have obtained documentation of the absence of sperm in the ejaculate or have had bilateral orchiectomy.

The following procedures apply for contraception and pregnancy avoidance.

1. Highly effective methods of contraception are defined as “those, alone or in combination, that result in a low failure rate (ie, less than 1% failure rate per year when used consistently and correctly). In this study, where medications and devices containing hormones are excluded, the only acceptable methods of contraception are:
 - Intrauterine device.
 - Bilateral tubal occlusion.
2. Unacceptable methods of contraception are:
 - Hormonal methods.
 - Periodic abstinence (eg, calendar, ovulation, symptothermal, post-ovulation methods).
 - Spermicides only.
 - Withdrawal.
 - No method at all.
 - Use of female and male condoms together.
 - Cap/diaphragm/sponge without spermicide and without condom.
 - Sexual abstinence is NOT an acceptable method of contraception.
3. Subjects will be provided with information on highly effective/effective methods of contraception as part of the subject informed consent process and will be asked to sign a consent form stating that they understand the requirements for avoidance of pregnancy, donation of sperm during the course of the study.

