 - c) that personal information (including personal health information) may be added to Takeda's research databases for purposes of developing a better understanding of the safety and effectiveness of the study drug(s), studying other therapies for patients, developing a better understanding of disease, and improving the efficiency of future clinical studies;
 - d) that subjects agree not to restrict the use and disclosure of their personal information (including personal health information) upon withdrawal from the study to the extent that the restricted use or disclosure of such information may impact the scientific integrity of the research; and
 - e) that the subject's identity will remain confidential in the event that study results are published.

25. Male subjects must use highly effective contraception (as defined in the informed consent) from signing the informed consent throughout the duration of the study and for 70 days after the last dose of study drug after last dose. If the partner or wife of the subject is found to be pregnant during the study, the investigator will offer the subject the choice to receive unblinded treatment information.
26. A statement that clinical trial information from this trial will be publicly disclosed in a publicly accessible website, such as www.ClinicalTrials.gov.

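### Contraception: a barrier method is required of the man in two places, but the consent elements require a highly effective method, which the protocol's own definition limits to two partner-used methods; the status of that list is unclear

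*Protocol*

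**What the plan says.** Four places in the protocol bear on this.

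- **7.1, criterion 5.** A nonsterilized man who is sexually active with a partner of childbearing potential qualifies if he "agrees to use barrier method of contraception (eg, condom with or without spermicide"). An asterisk on that method leads to a footnote: "Definitions and highly effective methods of contraception are defined in Section 9.1.9".
- **9.1.9.1.** Such men "must use barrier contraception (eg, condom with or without spermicidal cream or jelly"). For the partners the verb changes: "Females of childbearing potential who are partners of male subjects are also advised to use additional contraception", with a pointer to the list that follows.
- **9.1.9.2.** Highly effective means "less than 1% failure rate per year when used consistently and correctly". The text continues: "In this study, where medications and devices containing hormones are excluded, the only acceptable methods of contraception are", followed by two entries, intrauterine device and bilateral tubal occlusion. Hormonal methods head the unacceptable list.
- **Appendix C, item 25.** "Male subjects must use highly effective contraception (as defined in the informed consent").

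Criterion 5, 9.1.9.1 and item 25 all give the same period: from signing consent, through the study, and for 70 days after the last dose.

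**The concern.** Site staff must turn these sections into one instruction for each man. Section 9.1.9.3 requires continued guidance on the study's contraceptive requirements. Appendix A schedules that counselling at Screening, at check-in and at discharge. Section 9.1.9.2 has subjects sign that they understand what is required. If eligibility rests on a condom and the consent elements rest on a highly effective method, the same man can be admitted under one rule and asked to agree to another.

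What is at stake is the protection of partners and of any pregnancy, which 9.1.10 treats as immediately reportable if it occurs during active dosing or within 70 days after the last active dose. The GMLT result, the power and the analyses are not affected.

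**Working it through.** No statistical calculation applies. The check is a comparison of the texts.

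**1. How many standards are there?** Criterion 5 and 9.1.9.1 agree on a barrier method, mandatory for the man. The two-method list in 9.1.9.2 is the protocol's own account of highly effective, the term that item 25 uses. That makes two standards: barrier, and highly effective.

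**2. What status does the second standard have?**
- 9.1.9.1: advised, for the partner, on top of the condom.
- 9.1.9.2: exclusive ("the only acceptable methods of contraception are"), with no statement of whom it binds.
- Item 25: mandatory, for the man.

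**3. Where does a male condom alone fall?** It satisfies criterion 5 and 9.1.9.1. In 9.1.9.2 it is on neither list. It is not one of the two acceptable methods, and the unacceptable list names only male and female condoms used together. By the sole definition in the documents, a condom alone is therefore not highly effective, and a man relying on it may not meet item 25. Both listed methods are used by the partner, so item 25 read with 9.1.9.2 gives the man a duty that he cannot carry out himself.

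**4. Do the cross-references settle it?** No. The criterion 5 footnote sends the reader from the barrier method to 9.1.9 for highly effective methods. Section 9.1.9.1 points to a list of highly effective or effective methods, but 9.1.9.2 has no separate category of effective methods. The unacceptable list rejects a cap, diaphragm or sponge when used without spermicide and without a condom. That suggests some barrier combinations might count, which does not fit a two-entry exclusive list.

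**5. The hormone wording.** Only men are enrolled, so the statement that hormone-containing products are excluded can limit contraception only through partners, who receive no study drug. Section 7.4 restricts what subjects take, not partners, and Table 7.a has no separate hormone entry. A couple using a condom plus a hormonal partner method meets criterion 5, yet the partner's method is on the unacceptable list.

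**6. How many men, and for how long?**
- Planned: 6 in Part 1 + 40 in Part 2 = 46.
- Actual: SAP section 3.0 reports Part 1 complete and 12 enrolled in Part 2 when enrollment was paused and then not resumed. If Part 1 enrolled its planned 6, the total is 6 + 12 = 18. The rule applied only to those who were nonsterilized with a partner of childbearing potential, a number the documents do not give.
- Planned length in Part 2: about 21 weeks (21 × 7 = 147 days) to the follow-up contact on Day 9 of Period 5. The 70 days run from the last dose, on Day 2 of that period, so 9 − 2 = 7 days overlap: 147 + 70 − 7 = 210 days, about 30 weeks.
- SAP section 7.1 says no subject began Period 2, so the actual periods were shorter.

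**The case against.** The best defence is that 9.1.9.1 already assigns the roles: the man must use a condom, and the partner is advised to add a method from the list below. Both listed methods are the partner's, so the exclusive wording in 9.1.9.2 would only limit which additional methods count. On that reading a condom user does what criterion 5 and 9.1.9.1 ask, and the hormone wording puts no enforceable duty on the partner. Counselling under 9.1.9.3 also refers to condoms. Item 25 leaves its definition to a consent form that is not among the documents.

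Much of this stands. A reader might infer three separate standards (condom, the two listed methods, highly effective), but the listed methods are the protocol's definition of highly effective, so there are two. A reader might also infer that a condom user breaches 9.1.9. The documents do not show that, because 9.1.9.1 offers the list as advised, additional partner methods. Nor is a breach of item 25 shown, since the consent form may define the term differently.

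The defence does not remove the conflict. Item 25 says the man must, where 9.1.9.1 says the partner is advised. Section 9.1.9.2 does not say that its exclusive list is advisory. And the criterion 5 footnote attaches that list to the man's own barrier method.

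**Conclusion.** The point holds as an internal contradiction that should be reconciled. The protocol has two non-equivalent contraception standards, and the highly effective one is advised, exclusive or mandatory depending on the section. A man using condoms alone meets criterion 5 and 9.1.9.1 but may not meet Appendix C item 25.

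The word *may* rests on one assumption: that highly effective in the consent form means what 9.1.9.2 says. That cannot be checked here.

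The matter is more than clerical, because it determines what sites counsel and what subjects agree to on a partner and fetal safety question. It has no effect on the GMLT result, power or any analysis. The planned 46 subjects overstates the exposure, given the 12 enrolled in Part 2 when it stopped. No view is taken on which standard is right.

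**What to change.** Reconcile criterion 5 with its footnote, 9.1.9.1, 9.1.9.2 and Appendix C item 25 so that they:

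- state one requirement for the male subject, in the same terms throughout;
- say to whom the 9.1.9.2 list applies, and whether it is required or advised;
- say whether the hormone wording is meant to cover partners who are not dosed;
- carry the result into item 25 and the matching line of the consent form.

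The choice of standard belongs to the sponsor and the IRB. The cost is wording in these protocol sections and one line of the consent form, with the usual IRB review. No procedure, sample size or analysis changes. Since enrollment was not resumed, the practical benefit lies mainly in any later protocol that reuses this text.
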